Study treatment will continue for all patients until investigator-determined disease progression according to RECIST v1.1 that is confirmed by repeat scans 4-8 weeks later, unacceptable toxicity, death, patient or physician decision to withdraw, or pregnancy, whichever occurs first. Patients who experience disease progression must have scans repeated 4–8 weeks after initial documentation of progression to confirm disease progression. These results will be used as part of the exploratory analyses for assessing efficacy based on immune-modified RECIST. Tumor assessments are to continue according to schedule for patients who discontinue treatment for reasons other than confirmed disease progression. Clinically stable patients who have disease progression may continue, as described below.

Clinically stable patients who have a favorable benefit–risk ratio may continue study treatment following radiographic progression per RECIST v1.1, but approval will need to be provided by the Medical Monitor on a case-by-case basis. Patients who continue treatment beyond radiographic disease progression will be closely monitored. Treatment will be discontinued if clinical deterioration because of disease progression occurs at any time or if persistent disease growth is confirmed on follow-up scans performed 4-8 weeks later.

[figure not shown]
Patients who discontinue one study drug in Arm A may be able to continue the other study drug, per guidelines for management of specific adverse events provided in Section 5.1.5 and [Appendix 10](#). After treatment discontinuation, patients will be followed for disease progression if applicable and followed for survival until death, withdrawal of consent, or loss to follow-up, whichever occurs first. If a patient withdraws from the study, study staff may use a public information source (e.g., county records) to obtain information about survival status only.

This study will not allow for crossover to other study drug(s) at the time of progression.

All patients who discontinue from study treatment because of radiographic disease progression or any other reasons will be asked to complete the European Quality of Life 5-Dimension, 5-Level (EQ-5D-5L) questionnaire and the European Organisation for Research and Treatment of Cancer Quality of Life Questionnaire Core 30 (EORTC QLQ-C30), approximately every 28 days for 6 months after the last dose of study treatment.

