4.5.5 Tumor and Response Evaluations

All measurable and non-measurable lesions must be documented at screening (within 35 days prior to initiation of study treatment). Evaluation of tumor response conforming to RECIST v1.1 must then be documented every 8 weeks (± 1 week) from the date of first study drug administration (Day 1) through 18 months (80 weeks) and then every 12 weeks (± 1 week) thereafter, until investigator-determined disease progression (according to RECIST v1.1 that is confirmed 4–8 weeks after initial documentation of progression), withdrawal of consent, study termination by the Sponsor, or death, whichever occurs first. Thus, tumor assessments are to continue according to schedule for patients who discontinue treatment for reasons other than disease progression. At the investigator's discretion, tumor assessments may be repeated at any time if disease progression is suspected.

Tumor assessments must be performed independently of changes to the study treatment administration schedule (i.e., when treatment is withheld). If a tumor assessment has to be performed early or late, subsequent assessments should be conducted according to the original schedule based on the date of first study treatment administration on Day 1 of Cycle 1. The tumor assessment schedule is identical in both arms to avoid potential bias.

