4.1 ANALYSIS POPULATIONS

4.1.1 Randomized Population

The randomized population or intent-to-treat (ITT) population is defined as all randomized patients, whether or not the patient received the assigned treatment.

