4.4.1 Primary Efficacy Endpoint

The primary efficacy analysis will be the comparison of PFS, as determined by the IRC, between the two treatment arms using the stratified log-rank test at an overall 0.01 significance level (two-sided).

PFS is defined as the time from randomization to the first occurrence of disease progression, as determined by the IRC according to RECIST v1.1, or death from any cause, whichever occurs first. Data for patients who have not experienced disease progression or death will be censored at the last tumor assessment date. Data for patients with no post-baseline tumor assessment will be censored at randomization.

The HR for PFS will be estimated using a stratified Cox model and two-sided 95% CIs for the HR will be provided. Results from an unstratified analysis will also be provided. Kaplan-Meier methodology will be used to estimate the median PFS for each treatment arm, and Kaplan-Meier curves will be produced. The 95% CI of the median PFS for each treatment arm will be constructed using the Brookmeyer and Crowley method ([Brookmeyer and Crowley 1982](#)).

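### The PFS rule that censors patients without a post-baseline scan at randomization is not limited to event-free patients, so read literally it censors early deaths at day 0; never-dosed patients also lack a scan schedule

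*SAP*

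**What the plan says.** SAP 4.4.1 measures PFS from randomization to IRC-assessed progression "or death from any cause, whichever occurs first". Two censoring sentences follow. The first is restricted to event-free patients: "Data for patients who have not experienced disease progression or death will be censored at the last tumor assessment date". The second carries no such restriction: "Data for patients with no post-baseline tumor assessment will be censored at randomization".

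Protocol 6.4.1 and the synopsis use the same wording. SAP 4.4.2.3 applies the method to investigator-assessed PFS, and SAP 4.9 (Missing Data) only refers back to these sections.

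On never-dosed patients, SAP 4.1.1 defines the ITT population as "all randomized patients, whether or not the patient received the assigned treatment". Protocol 4.5.5 sets the scan calendar as "every 8 weeks (± 1 week) from the date of first study drug administration (Day 1) through 18 months (80 weeks"). For patients who stop treatment, "tumor assessments are to continue according to schedule for patients who discontinue treatment for reasons other than disease progression", and protocol 3.1.1 adds: "After treatment discontinuation, patients will be followed for disease progression if applicable and followed for survival until death". Protocol 4.2 asks for the first dose within 3 days of randomization, but the Medical Monitor may approve a longer gap.

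**The concern.** The first scheduled scan is at Week 8. A patient who dies earlier, with no unscheduled scan, is an event under the PFS definition and a day-0 censored observation under the second censoring sentence. Two competent programmers could build different primary datasets from the same text.

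The parallel OS rule in SAP 4.4.2.1 does not have this problem. It depends on survival information, which a recorded death supplies. The PFS rule depends on a tumor assessment, which a death does not supply.

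What is at stake is informative censoring. Early deaths are unambiguous failures, and removing them at time zero hides any imbalance in early mortality between the arms.

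The secondary issue is that a randomized patient who never starts treatment has no first-dose date from which to count scans, and the follow-up text is written for patients who stop treatment. The trial is open-label, so refusal after allocation could depend on the arm. That is an inference; the documents give no data on it.

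**Working it through.** **1. Inputs.** SAP 2.3: 240 PFS events, two-sided alpha 0.01, median PFS 5.5 vs 10.0 months (HR 0.55), median OS 28 vs 37.5 months. SAP section 2: 225 patients per arm. Protocol 4.5.5: first scan at Week 8 ± 1 week.

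**2. The plan's own figure.** Schoenfeld power is Φ(½·√240·|ln 0.55| − 2.576) = Φ(4.631 − 2.576) = Φ(2.055) = 98.0%. The largest significant HR is exp(−2 × 2.576/√240) = 0.717. Both match the stated 98% and 0.72.

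**3. Deaths before the first scan, literal reading.** With exponential OS, deaths per arm are 225 × (1 − 2^(−t/median)). Week 8 is 56/30.4375 = 1.84 months.
- Control: 225 × (1 − 2^(−1.84/28)) = 10.0
- Combination: 225 × (1 − 2^(−1.84/37.5)) = 7.5
- Total 17.5, and 17.5/240 = 7.3%
- First scan at Week 7: 15.4 deaths (6.4%). At Week 9: 19.7 deaths (8.2%).

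**4. Power if those events are lost and not replaced.** At 240 − 17.5 = 222.5 events, power is Φ(½·√222.5·0.598 − 2.576) = 97.0%, and the largest significant HR is about 0.71. Over Weeks 7 to 9, power is 97.2% to 96.9%.

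**5. Bias.** This was simulated with 3,000 trials per row, 225 per arm, exponential PFS, uniform 12-month accrual, a fixed 17-month cutoff, no dropout, and an unstratified log-rank test at two-sided 0.01. The early-death rates in rows 1 to 3 are assumptions, with HR 0.72 in the other patients. Row 4 uses the plan's PFS medians and the early-death rates from step 3. Cells show median HR and power.

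| Early deaths, control vs combination | Deaths counted | Literal censoring |
|---|---|---|
| 3% vs 6% | 0.76, 41% | 0.72, 59% |
| 3% vs 9% | 0.80, 27% | 0.72, 58% |
| 4.5% vs 4.5% | 0.73, 56% | 0.72, 59% |
| 4.45% vs 3.34% | 0.56, 98.7% | 0.55, 98.6% |

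The two rules diverge materially only when early deaths are unbalanced. Literal censoring then removes the imbalance from the estimate.

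**6. Never-dosed patients.** No rate is given. An assumed 1–5% of 450 is 4.5 to 22.5 patients. If events fall in proportion (237.6 to 228), power is 97.9% to 97.4%.

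**The case against.** The strongest defence is that the second censoring sentence is simply a sub-case of the first: event-free patients who have no last assessment date to use. SAP 4.4.5 supports this indirectly. It censors deaths that follow two or more missed scans only in a sensitivity analysis, and only if more than 5% of patients are affected, so those deaths are events in the primary analysis. This stands as a reason to think that early deaths were meant to count. A reader might infer that the plan definitely censors every early death; the documents do not support that. But 4.4.5 does not settle the matter, because a patient who dies before Week 8 has missed no scan.

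A reader might also infer that never-dosed patients drop out of the ITT analysis. They do not. SAP 4.1.1 and 4.4 keep them, and a known death counts under the PFS definition. Protocol 3.2 has all enrolled patients followed to death, withdrawal of consent or loss to follow-up unless the Sponsor ends the trial, and unscheduled scans are allowed. Where refusal comes with withdrawal of consent, no schedule would recover scans (protocol 4.6.1). What remains is that routine scans for this group are unspecified.

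The size is also open to challenge, and this stands. Eligibility requires life expectancy of at least 3 months and ECOG 0–1, and some early deaths will have had an early or unscheduled scan. The analysis is event-driven, so most lost events would be replaced by later ones.

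Finally, SAP version 3 reports that the primary endpoint was not met and that the study is ending early. A new scan calendar can no longer affect that analysis. The question of which rule was programmed remains.

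**Conclusion.** The primary endpoint text conflicts with itself, and the conflict should be resolved in writing. Read literally, it affects up to about 15–20 deaths, or 6–8% of 240 events. This is an upper bound that rests on exponential OS at the planned medians and on no scan before death. The loss of power is about one percentage point. The main risk is bias if early deaths differ by arm, and that was shown only under assumed rates. With the plan's own split of 10.0 and 7.5 deaths, the two rules give nearly the same answer.

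The never-dosed gap is real but secondary and of unknown size. A reader might infer that either issue changed the reported outcome. The documents state neither the rule programmed nor the relevant counts, so that inference is not supported.

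**What to change.** In SAP 4.4.1 and protocol 6.4.1, replace the second censoring sentence with:

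> Patients who are alive and progression-free and have no post-baseline tumor assessment will be censored at randomization; death before any post-baseline assessment is an event on the date of death.

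Confirm which rule was programmed for the primary analysis, and report the number of patients censored at day 0 by arm.

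For randomized, never-dosed patients, state in protocol 4.5.5 that tumor assessments run from randomization unless consent is withdrawn. Confirm their survival follow-up before the final OS analysis at database lock, and report their number by arm. The calendar for dosed patients can stay as it is.

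The cost is a sentence or two, a check of the analysis program and one small table. If early deaths were censored, the primary analysis should be rerun with them as events and both results shown. The scan-schedule wording comes too late to affect the primary analysis.

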4.4.2 Secondary Efficacy Endpoints

4.4.2.1 Overall Survival

OS is defined as the time from randomization to death from any cause. For patients who are alive at the time of analysis data cutoff, OS time will be censored at the date the patient was last known to be alive. Survival time for patients with no post-baseline survival information will be censored at randomization. The HR for OS will be estimated using a stratified Cox model, and a two-sided 95% CI for the HR will be provided. Results from an unstratified analysis will also be provided. The Kaplan-Meier approach will be used to estimate median OS and 2-year landmark survival rate. The 95% CI of the median OS will be estimated using the Brookmeyer and Crowley method ([Brookmeyer and Crowley 1982](#)). The 95% CI of landmark survival rate will be calculated using the standard error derived from Greenwood's formula ([Greenwood 1926](#)).

4.4.2.2 Objective Response Rate by IRC and Investigator Using RECIST v1.1

Objective response rate is defined as the total number of patients whose objective response is a complete response or a partial response, divided by the number of patients in the ITT population with measurable disease at baseline. Objective response is defined as a complete response or partial response on two consecutive occasions ≥ 4

weeks apart, as determined by the IRC and or investigator using RECIST v1.1. A 95% Clopper-Pearson CI will be calculated for the ORR for each treatment arm. The difference in ORR between treatment arms will be tested using the stratified Cochrane-Mantel-Haenszel test. A 95% Hauck-Anderson CI will be calculated for the difference in ORR between treatment arms.

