---------	---	----

LIST OF FIGURES

Figure 1	Study Schema.....	8
----------	-------------------	---

LIST OF APPENDICES

Appendix 1	Protocol Synopsis	24
Appendix 2	Schedule of Assessments.....	37
Appendix 3	Schedule of Pharmacokinetic, Immunogenicity, and Biomarker Samples.....	48
Appendix 4	Response Evaluation Criteria in Solid Tumors, Version 1.1.....	49

1. **BACKGROUND**

This Statistical Analysis Plan (SAP) provides details of the planned analyses and statistical methods for Study CO39722 (IMspire170): A Phase III, open-label, multicenter, two-arm, randomized study to investigate the efficacy and safety of cobimetinib plus atezolizumab versus pembrolizumab in patients with previously untreated advanced *BRAF*^{V600} wild-type melanoma. The background for the study can be found in the study protocol.

It is anticipated that positive results from Study CO39722 will support the submission of filing applications globally for the use of cobimetinib plus atezolizumab for the treatment of patients with previously untreated advanced *BRAF*^{V600} wild-type melanoma. For purposes of registration, the analyses outlined in this SAP will supersede those specified in the protocol.

2. **STUDY DESIGN**

[figure not shown]
Study CO39722 is a Phase III, multicenter, open-label, randomized study designed to evaluate the efficacy, safety, and pharmacokinetics of cobimetinib plus atezolizumab compared with pembrolizumab in treatment-naive patients with advanced *BRAF*^{V600} wild-type melanoma.

This study will be conducted globally and approximately 450 patients will be randomized in a 1:1 ratio to one of two treatment arms:

- Arm A: Patients will receive 60 mg of cobimetinib by mouth (PO) on a 21 days on, 7 days off (21/7) schedule (dosing on Days 1-21, followed by no dosing on Days 22-28) plus 840 mg of atezolizumab by intravenous (IV) infusion on Days 1 and 15 of each 28-day cycle (n=225).
- Arm B: Patients will receive 200 mg of pembrolizumab administered by IV infusion every 3 weeks (Q3W) (n=225).

The study schema is presented in [Figure 1](#).

Figure 1 Study Schema

PD=progressive disease; PD-L1=programmed death–ligand 1; Q3W=every 3 weeks; Q2W=every 2 weeks, R=randomization; RECIST v1.1=Response Evaluation Criteria in Solid Tumors, Version 1.1; 21/7=21 days on/7 days off (schedule).

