2.3 DETERMINATION OF SAMPLE SIZE

Approximately 450 patients will be randomized into the study.

The overall type I error (α) for this study is 0.05 (two-sided). Formal treatment comparisons will be performed by first evaluating the primary endpoint of IRC-assessed PFS (per RECIST v1.1) at $\alpha=0.01$ (two-sided). If PFS is statistically significant at $\alpha=0.01$, then the key secondary endpoints will be evaluated at $\alpha=0.05$ (two-sided) in a hierarchical manner in the following order: OS, IRC-assessed objective response rate (ORR), and landmark OS. IRC-assessed ORR and landmark OS will be tested when OS crosses the pre-specified boundary.

The type I error (α) for the analysis of the primary endpoint of IRC-assessed PFS is 0.01 (two-sided). The analysis of the primary endpoint of IRC-assessed PFS will take place when approximately 240 PFS events have occurred. Statistical considerations are based on the following assumptions:

- Stratified log-rank test at 0.01 significance level (two-sided)
- Median PFS of 5.5 months for the pembrolizumab arm
- Median PFS of 10.0 months for the cobimetinib plus atezolizumab arm
- Enrollment period of approximately 12 months
- Annual dropout rate of 5%
- No interim analysis for PFS

A total of 240 PFS events provides approximately 98% power to detect an improvement in median PFS from 5.5 months in the pembrolizumab arm to 10.0 months in the cobimetinib plus atezolizumab arm. This corresponds to a hazard ratio (HR) of 0.55, with a minimal detectable difference of 0.72. The PFS analysis will be conducted approximately 17 months after first patient in (FPI). The final analysis of the secondary endpoint of OS will be performed after the occurrence of approximately 295 deaths. A total of 295 deaths provides approximately 60% power to detect an improvement in median OS from 28 months in the pembrolizumab arm to 37.5 months in the cobimetinib plus atezolizumab arm, corresponding to an HR of 0.75, or 80% power to detect an HR of 0.70. Two interim analyses of OS will be conducted. The final OS analysis will be conducted approximately 68 months after FPI.

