4.4 EFFICACY ANALYSIS

Unless otherwise noted, efficacy analyses will include all randomized patients, and patients will be grouped according to the treatment assigned at randomization. The stratification factors will be those used for randomization and will be obtained from the IWRS (PD-L1 status, baseline serum LDH level and geographic region). Due to the potential risk of over-stratification ([Akazawa et al. 1997](#)), if at least one stratum (i.e., a combination of stratification factor levels across PD-L1 status, baseline serum LDH level and geographic region) has fewer than 10 IRC-assessed PFS events across treatment arms, the stratification factor (one of three stratification factors: PD-L1 status, baseline

serum LDH level and geographic region per IWRS) which contains the level with the smallest number of patients will be removed from the stratified analyses. The removal of the stratification factors will continue until there is no stratum with fewer than 10 IRC-assessed PFS events. The final set of stratification factors used in stratified analyses will be applied to all endpoints where stratified analyses are planned.

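### ORR is tested by a stratified CMH test, but its difference gets only an unstratified Hauck-Anderson interval: mildly conservative, able to cover zero when the test rejects, and a minor reporting matter now that PFS was not met

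*SAP*

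**What the plan says.** SAP 4.4.2.2 sets the denominator ("divided by the number of patients in the ITT population with measurable disease at baseline"), gives each arm a Clopper-Pearson interval, and then makes two statements about the comparison. The first is the test: "The difference in ORR between treatment arms will be tested using the stratified Cochrane-Mantel-Haenszel test". The second is the interval: "A 95% Hauck-Anderson CI will be calculated for the difference in ORR between treatment arms". No stratified estimate of the difference is named, and nothing says how to read the two results if they disagree.

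SAP 4.4 derives one final set of stratification factors, after removing factors where strata have too few events. That set "will be applied to all endpoints where stratified analyses are planned". For PFS (SAP 4.4.1) and OS (SAP 4.4.2.1) the plan gives a stratified hazard ratio with a 95% CI, with an unstratified analysis alongside. ORR has no such pair. Protocol 6.4.2 specifies the stratified CMH test but no interval for the difference, so the Hauck-Anderson interval first appears in the SAP.

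IRC-assessed ORR is one of the endpoints covered by SAP 2.3: if PFS is significant, "then the key secondary endpoints will be evaluated at $\alpha=0.05$ (two-sided) in a hierarchical manner". It comes after OS: "IRC-assessed ORR and landmark OS will be tested when OS crosses the pre-specified boundary". SAP 2.5 (version 3) records that the primary endpoint was not met.

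**The concern.** The p-value and the interval describe the same contrast but rest on different variance models. CMH compares arms within strata. The standard Hauck-Anderson interval pools over strata and adds a continuity correction. (The SAP uses neither word, unstratified or continuity-corrected; these are properties of the method it names.)

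Pooling matters when the strata predict response. Pooled binomial variance equals the average within-stratum variance plus the variance of the response rates between strata. Stratified randomisation keeps the between-stratum part out of the arm comparison, yet the pooled standard error still counts it. Protocol 3.3.10 gives reason to expect some effect: it treats PD-L1 as strongly prognostic and linked to outcome on this drug class, and LDH as strongly prognostic for long-term survival.

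What is at stake is the reported precision of the ORR difference, and a possible report in which a nominally significant p-value sits beside an interval that includes zero. The same pairing applies to investigator-assessed ORR and, through SAP 4.4.3.1, to immune-modified RECIST response.

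**Working it through.** **Plan's own figure.** The plan states no ORR power, effect size or interval width, so there is no ORR figure to reproduce. Its PFS design figure does reproduce: Φ(|ln 0.55|·√240/2 − 2.576) = Φ(2.055) = 0.98.

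**Inputs**
- 225 per arm: "approximately 450 patients will be randomized in a 1:1 ratio to one of two treatment arms" (SAP 2). Measurable disease is an entry criterion (Protocol 4.1.1.1), so the ORR denominator is taken as 225.
- Control ORR 32.9%: the historical pembrolizumab figure in Protocol 3.3.2.
- Experimental ORR 32.9% to 50%: an assumed range. The upper end is the Phase Ib result in 10 patients (Protocol 1.3.5.1.1).
- Strata: 2 × 2 × 3 = 12 before any removal under SAP 4.4.
- Stratum shares and response rates: assumptions. Control ORR across strata is constant (none), 16–49% (moderate) or 8–63% (strong).

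**Formulas**
- Hauck-Anderson: d ± [1/(2·min n) + 1.96·√(p₁q₁/(n₁−1) + p₂q₂/(n₂−1))].
- Wald: d ± 1.96·√(p₁q₁/n₁ + p₂q₂/n₂).
- Stratified: Mantel-Haenszel-weighted risk difference with Sato variance.

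**Step 1: the correction alone.** 1/(2·225) = 0.22 points. At 32.9% vs 45%:
- Hauck-Anderson half-width: 0.0022 + 1.96·√[(0.2208 + 0.2475)/224] = 9.18 points.
- Wald half-width: 1.96·√[(0.2208 + 0.2475)/225] = 8.94 points.

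The ratio is 1.027. With no stratum effect, exact Hauck-Anderson coverage over the response rates checked is 95.4–95.6% (Wald 94.9%).

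**Step 2: adding the strata, by hand.** Take four equal strata with assumed response rates 50, 32, 28 and 12%, the same in both arms.
- Mean rate 30.5%; pooled variance 0.305·0.695 = 0.2120.
- Between-stratum variance (0.195² + 0.015² + 0.025² + 0.185²)/4 = 0.0183.
- Pooled to within-stratum standard error: √[0.2120/(0.2120 − 0.0183)] = 1.046.
- The correction and n−1 denominators add a factor of 1.028 at this rate: (0.0022 + 1.96·√(2·0.2120/224)) / (1.96·√(2·0.2120/225)) = 0.0875/0.0851.
- Product: about 1.075, or 7–8% wider.

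**Step 3: simulation, 12 strata, 400,000 trials per scenario.**

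| | No stratum effect | Moderate | Strong |
|---|---|---|---|
| Stratified half-width, 32.9% vs 45% (points) | 8.92 | 8.69 | 8.29 |
| Hauck-Anderson excess width | 2.7% | 5.5% | 10.6% |
| Hauck-Anderson coverage | 95.5% | 96.0% | 96.8% |
| CMH rejects, interval covers 0: null | 0.5% | 1.0% | 1.8% |
| same, 32.9% vs 42% | 1.6% | 3.7% | 7.7% |
| same, 32.9% vs 45% | 1.2% | 2.9% | 5.7% |
| same, 32.9% vs 50% | 0.4% | 0.8% | 1.3% |

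The mean Hauck-Anderson half-width at 32.9% vs 45% is about 9.16 points, so the excess is roughly 0.2 to 0.9 points per side. The reverse conflict (interval excludes zero, CMH does not reject) rounds to 0.0% throughout. Under the null with strong strata CMH rejects in 5.0% of trials.

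Separate runs at an odds ratio of 1.5 with four strata agree: the interval is about 2.5–2.7% wider with no stratum effect and 7–8% wider at the Step 2 rates, with the conflict in about 1% to 6% of trials.

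**Step 4: which feature causes it.** Dropping the correction but staying unstratified still leaves the conflict at 1.9% (moderate) and 5.6% (strong) at 32.9% vs 42%. Most of it comes from not stratifying.

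**Step 5: after the change.** The stratified interval covers 94.8–94.9%. CMH rejecting while it covers zero falls to 0.05% of trials or less; the reverse is 0.06–0.46%.

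**The case against.** The strongest reply is that nothing confirmatory depends on this interval. SAP 4.4.2.2 assigns the test to CMH, and no section uses the interval for a decision. A reader might infer that the mismatch threatens the ORR conclusion or its error rate. The documents do not support that: the CMH decision and type I error are untouched, and with PFS not met the SAP 2.3 hierarchy never reaches a formal ORR test. This stands, and it sets the severity.

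A reader might also infer that the interval is simply too wide. That is not supported as a flat statement. With no stratum effect its coverage is close to nominal, and the larger excess rests on stratum response rates found in no document. Protocol 3.3.10 speaks of prognosis and outcome and gives no ORR by stratum. The removal rule in SAP 4.4 could also drop LDH or PD-L1, which would shrink the gain from stratifying.

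Nor does SAP 4.4 contradict 4.4.2.2. It applies the final factors where a stratified analysis is planned, and no stratified ORR interval is planned.

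An unstratified difference has a real merit: it equals the subtraction of the two arm ORRs printed beside it. That is a reason to keep it, but not to make it the only interval accompanying a stratified test. The error is conservative and runs one way, against claiming benefit. Still, without a confirmatory ORR test any CMH p-value is nominal, and readers will look to the estimate and its interval.

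**Conclusion.** The point holds as a minor consistency issue. ORR has a stratified test without a stratified estimate or interval, unlike PFS and OS. The Hauck-Anderson interval is mildly conservative: about 2.5–3% wider than a stratified interval if the strata do not predict response, and about 5–11% wider if they predict it moderately to strongly. At modest effects it covers zero while CMH rejects in roughly 1–8% of trials, with essentially no conflict the other way. At 32.9% vs 50% the figure is about 1% or less.

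These sizes assume 225 evaluable patients per arm, a control ORR of 32.9%, and stratum shares and response rates that the documents do not supply. The direction does not depend on those choices; the size does. The consequence is confined to the reported precision of the ORR difference.

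**What to change.** In SAP 4.4.2.2, add a stratified difference in ORR with a 95% CI (Mantel-Haenszel-weighted or stratified Miettinen-Nurminen), using the final stratification factors from SAP 4.4 so that it matches the CMH test. Keep the pre-specified Hauck-Anderson interval and label it unstratified and supportive. Apply the same to investigator-assessed and immune-modified RECIST response.

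SAP version 3 was written after the primary result was known, and neither amendment rationale mentions ORR. The stratified interval should therefore be documented as an addition, with the pre-specified interval still shown, rather than as a silent replacement by a narrower one.

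The cost is a sentence or two in the SAP, a standard software option and one more interval to report. The stratified difference may not equal the simple subtraction of the two arm ORRs; a table footnote should say so.
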